### 6.2.5 Cardiac toxicity

If any of the following cardiac toxicities occur, participants will be removed from protocol:

- Uncontrolled arrhythmia
- Grade 3 or 4 Congestive heart failure

### 6.2.6 Gastrointestinal toxicity

- Mucositis, dysphagia and diarrhea:

For  $\geq$  Grade 3 gastrointestinal toxicities mentioned above, treatment will be held until toxicity decreases to  $\leq 1$  or baseline, after which treatment will be resumed at full dose. Treatment may be held for a maximum of 2 weeks, after which participants will be removed from study.

- Constipation:

Start stool softeners and mild bowel stimulants (docusate sodium 100 mg po tid plus senna and/or psyllium and/or milk of magnesia and/or Miralax). Increase regimen and add additional agents as needed.

### 6.2.7 Peripheral nervous system toxicity

PERIPHERAL NERVOUS SYSTEM TOXICITY		
Grade	Brentuximab dose	Comments
Grade 1	1.2 mg/kg (100%)	
Grade 2	Reduce dose to 0.8 mg/kg.	
Grade 3	Withhold dose until toxicity is < Grade 2 or has returned to baseline. Resume at a dose of 0.8 mg/kg. If dose has already been reduced to 0.8 mg/kg, reduce dose to 0.6 mg/kg.	While brentuximab is held, the other agents will continue as described, provided treatment criteria are met. The dose of brentuximab will not be re-escalated.
Grade 4	-----	Patient to come off of study

### 6.2.8 Infusion reactions:

Infusion reactions are relatively uncommon (11% of patients in phase II studies). Pre-treatment is not required, however, investigators will add supportive medications during a reaction and with subsequent cycles, as indicated. Patients with prior hypersensitivity reactions must be pre-medicated for hypersensitivity in subsequent cycles as per institutional routine for monoclonal antibody therapy.

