## 5.2 Duration of Therapy

Duration of therapy will depend on individual response and toxicity. In the absence of disease progression or unacceptable toxicity, treatment will continue for 4 to 6 total cycles of brentuximab/AD, depending on treatment response or until one of the following criteria applies:

- Disease progression
- Intercurrent illness that prevents further administration of treatment
- Unacceptable adverse event(s), including Grade 4 neuropathy or other Grade 4 events felt to be related to brentuximab
- Any toxicity requiring dose delays of greater than 2 weeks
- Participant demonstrates an inability or unwillingness to comply with the regimen and/or documentation requirements
- Participant decides to withdraw from the study
- General or specific changes in the participant's condition render the participant unacceptable for further treatment in the opinion of the treating investigator

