## 5.3 Criteria for Removal from Study Treatment

Participants will be removed from study treatment when intercurrent illness, toxicity, inability to participate or a change in condition occurs. The reason for treatment removal and the date the participant was removed must be documented in the study-specific case report form (CRF). Alternative care options will be discussed with the participant.

In the event of unusual or life-threatening complications, participating investigators must immediately notify the Principal Investigator/Sponsor, [name] at [contact].

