## 6. EXPECTED TOXICITIES AND DOSING DELAYS/DOSE MODIFICATIONS

Dose delays and modifications will be made using the following recommendations. Toxicity assessments will be done using the CTEP NCI Common Terminology Criteria for Adverse Events (CTCAE) version 4.0, which is identified and located on the CTEP website at: [http://ctep.cancer.gov/protocolDevelopment/electronic\\_applications/ctc.htm](http://ctep.cancer.gov/protocolDevelopment/electronic_applications/ctc.htm).

If possible, symptoms should be managed symptomatically. In the case of toxicity, appropriate medical treatment should be used (including anti-emetics, anti-diarrheals, etc.).

All adverse events experienced by participants will be collected from the time of the first dose of study treatment, through the study and until the final study visit. Participants continuing to experience toxicity at the off study visit may be contacted for additional assessments until the toxicity has resolved or is deemed irreversible.

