### 6.2.9 Other Brentuximab toxicities:

All other Grade 3-4 toxicity considered possibly, probably, or definitely related to brentuximab (Not including hematologic, cardiac, hepatic, gastrointestinal, peripheral nervous system, or alopecia).

Subjects will be removed from study treatment if a second episode of grade 3-4 toxicity occurs despite dose reduction according to table below.

CONFIDENTIAL

This document is confidential. Do not disclose or use except as authorized.

OTHER TOXICITY			
Grade	Brentuximab dose	AD doses	Comments
Grade 1	1.2 mg/kg (100%)	100%	
Grade 2	1.2 mg/kg (100%)	100%	
Grade 3	Withhold dose until toxicity is $\leq$ Grade 2 or has returned to baseline. Reduce the dose to 0.8 mg/kg. If a second dose reduction is required, dose will be reduced to 0.6 mg/kg.	Withhold dose until toxicity is $\leq$ Grade 2 or has returned to baseline, then resume at full dose.	The dose of brentuximab will not be re-escalated.
Grade 4	Withhold dose until toxicity is Grade $\leq 2$ or has returned to baseline, then reduce dose to 0.8 mg/kg and resume treatment, or discontinue at the discretion of the investigator. If a second dose reduction is required, dose will be reduced to 0.6 mg/kg, or discontinue at the discretion of the investigator.	Withhold dose until toxicity is Grade $\leq 2$ or has returned to baseline, then resume at full dose.	The dose of brentuximab will not be re-escalated.

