#### 7.1.7 Administration

Dose and frequency will be administered per study protocol. Dosing should be based on the participant's pre-dose weight determined at day 1 visit of each cycle. Dose may be re-calculated based on weight on day 15 if that is consistent with the institutional standard of care. Brentuximab dose should be rounded to the nearest whole number of milligrams. Infusion time for brentuximab is 30 minutes. The drug may be given at slower infusion at the discretion of the treatment team in the setting of prior hypersensitivity reactions, consistent with institutional standards.

CONFIDENTIAL

This document is confidential. Do not disclose or use except as authorized.

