#### 13.1.3 Evaluation of toxicity

All participants will be evaluable for toxicity from the time of their first treatment. Participants will be assessed for toxicity with each treatment and participants with unacceptable toxicity will be removed from the study. All participants who receive treatment, regardless of eligibility, will be evaluated for toxicity.

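### Protocol 5.2 and 6.2.9 give different instructions for brentuximab-related grade 4 events, and the hypersensitivity rules in 6.2.8 and 7.1.7 do not except anaphylaxis

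*Combined protocol and SAP*

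**What the plan says.** **Grade 4 events.** Protocol 5.2 lists the criteria that end treatment. One of them reads "Unacceptable adverse event(s), including Grade 4 neuropathy or other Grade 4 events felt to be related to brentuximab". Section 6.2.9 covers all other related grade 3-4 toxicity. It excludes hematologic, cardiac, hepatic, gastrointestinal and peripheral nervous system toxicity, and alopecia. Its grade 4 row has brentuximab withheld until recovery to grade 2 or lower, or baseline, and "then reduce dose to 0.8 mg/kg and resume treatment, or discontinue at the discretion of the investigator".

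**Hypersensitivity.** Section 6.2.8 says "Patients with prior hypersensitivity reactions must be pre-medicated for hypersensitivity in subsequent cycles as per institutional routine for monoclonal antibody therapy". Section 7.1.7 adds "The drug may be given at slower infusion at the discretion of the treatment team in the setting of prior hypersensitivity reactions". The nursing page at the end of the document sends staff to 6.2.8 for infusion reactions and repeats the slower-infusion option.

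**Other serious events.** Sections 5 to 7 do not name SJS/TEN or PML. The 6.2.9 table gives full dose at grades 1 and 2. At grade 3 the drug is withheld and then restarted lower: "Reduce the dose to 0.8 mg/kg. If a second dose reduction is required", the next step is 0.6 mg/kg. Section 6.2.9 requires removal from treatment only at a second grade 3-4 episode despite dose reduction.

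**General exits.** Section 5.2 also stops treatment for a toxicity delay of more than two weeks, or when the investigator thinks the patient's condition no longer permits it. Section 13.1.3 says "participants with unacceptable toxicity will be removed from the study". Section 5.3 provides for removal for toxicity and adds: "In the event of unusual or life-threatening complications, participating investigators must immediately notify the Principal Investigator/Sponsor".

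**Attached prescribing information.** Its section 5.2 requires permanent discontinuation for anaphylaxis. Its 5.9 says to hold for suspected PML and discontinue if it is confirmed. Its 5.11 says to discontinue for SJS or TEN. None of these carries a grade threshold.

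**The concern.** A dosing rule should give one answer for one event. For a related grade 4 toxicity under 6.2.9, the protocol gives two. In a multi-center trial, one site can stop the patient and another can resume, with neither in deviation.

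The hypersensitivity text has a different fault. The label pairs premedication after an infusion reaction with an absolute stop for anaphylaxis. The protocol carries the first half and not the second, and staff are directed to that text. What is at stake is a second exposure after anaphylaxis in a patient with a highly curable disease. For SJS/TEN and PML, the label describes fatal outcomes.

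The choice of rule also reaches the trial's data. Discontinuation due to toxicity is part of a secondary endpoint (1.4.2). Under 13.1.1 and 13.1.4, a patient removed before initial restaging for a reason other than progression is not evaluable for response.

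**Working it through.** The plan states no figure on this point, so there is nothing to reproduce. The check traces each event through the text and then sizes the grade 4 conflict.

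**Step 1: trace the events.**

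| Event | Protocol rule that reaches it | Attached label |
|---|---|---|
| Related grade 4 event under 6.2.9 | 5.2: treatment ends. 6.2.9: resume at 0.8 mg/kg or discontinue, by discretion | No general grade 4 rule is relied on here |
| Anaphylaxis | 6.2.8: premedicate. 7.1.7: may slow the infusion. If grade 3-4 and related, the 6.2.9 table also applies | Permanent discontinuation |
| SJS/TEN, first episode below grade 4 | 6.2.9: full dose at grades 1-2; hold, then 0.8 mg/kg at grade 3 | Discontinue |
| PML, first episode below grade 4 | As for SJS/TEN; no hold for suspected PML | Hold if suspected, discontinue if confirmed |

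*Precedence.* Section 5 refers the reader to Section 6 for dose modifications but sets no order between them. Section 6.2.3 gives full dose to an afebrile patient with ANC below 500, and 10.4.1 calls grade 4 neutropenia expected. That suggests specific Section 6 rules may be meant to qualify 5.2, but no text says so.

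*Anaphylaxis that resolves the same day.* The two-week delay criterion is not met. The mandatory removal in 6.2.9 needs a second grade 3-4 episode after dose reduction, so it acts only after re-exposure. What remains is the judgement that the event was unacceptable, or the disputed grade 4 rule.

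*SJS/TEN and PML.* To resume, the event must be a first episode below grade 4, must recover without a delay of more than two weeks, and must not be judged unacceptable. The path is narrow.

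**Step 2: size of the grade 4 conflict.** Inputs are the grade 4 counts in the 6.1.1 table, leaving out the categories that 6.2.9 excludes.

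- Hodgkin lymphoma (HL): pulmonary embolism 2 + pneumonitis 1 = 3 of 102 = 2.94%. The Clopper-Pearson 95% interval is 0.61% to 8.36%. Multiplied by 34: 1.0 patient (0.21 to 2.84).
- Adding ALCL fatigue 1, syncope 1 and pain in extremity 1: 6 of 160 = 3.75% (1.39% to 7.98%). Multiplied by 34: 1.28 patients (0.47 to 2.71).

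**Step 3: why this is not a bound.** The table lists only terms seen in at least 2 patients. Its HL grade 4 counts are neutropenia 6, thrombocytopenia 2, anaemia 1, abdominal pain 1, pulmonary embolism 2 and pneumonitis 1. They sum to 13, against 14 HL patients with any grade 4 event, so at least one patient had an unlisted term. In the other direction, the table is of treatment-emergent events and does not state relatedness. The intervals cover sampling error only.

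**Step 4: the named events.** Section 6.1 of the label reports two anaphylaxis cases in phase 1, without a denominator, and no rate for SJS/TEN or PML. No rate can be derived.

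**The case against.** The strongest reply is that the protocol is not silent. The generic 6.2.9 table reaches all three named events at grade 3-4, because infusion, skin and central nervous system events are not among its exclusions. It holds, reduces, and removes the patient on recurrence. A life-threatening reaction must be notified at once under 5.3, and 5.2, 5.3 and 13.1.3 let an investigator stop for any unacceptable toxicity. The label is in the same file. Section 6 also describes itself as guidance: "Dose delays and modifications will be made using the following recommendations".

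Much of that stands. A reader might infer that the protocol directs re-dosing after anaphylaxis. It does not: 6.2.8 sets a condition for patients who are re-dosed, and the gap is the missing prohibition. A reader might also infer that no rule exists for the three events, or that 6.2.9 never mandates a stop. The table and its second-episode removal contradict both.

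The reply does not close the point. The general exits rest on judgement and name none of the events. Notifying the sponsor is not a dosing rule. The protocol body cites the package insert to define expectedness (10.1.3), not dosing. Calling Section 6 recommendations does not explain the gap, since it sets mandatory named stops elsewhere (6.2.5, and grade 4 neuropathy in 6.2.7). A sponsor may depart from a label, and this one does so with event-specific rules for neuropathy and neutropenia. For these three events there is only the generic table, or in 6.2.8 a premedication rule, and no sign of a deliberate choice.

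**Conclusion.** The point holds as a minor safety correction. The grade 4 conflict and the missing anaphylaxis exception carry it; SJS/TEN and PML are a lesser addition.

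The grade 4 conflict may touch roughly one of 34 patients. That assumes one patient per event, every event related to brentuximab, every event falling under 6.2.9, and single-agent 1.8 mg/kg rates carrying over to this combination at 1.2 mg/kg. It is an order of magnitude only. The named events are rare and unquantified.

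Two further inferences are not supported. One is that 5.2 must prevail and the 6.2.9 resume option is an error. The documents set no order, and 6.2.3 hints at the reverse. The other is that the wording cannot affect the endpoints. A toxicity stop before first restaging makes a patient non-evaluable for response, and 13.1.4 does not offer replacement for toxicity, so one such stop takes the evaluable number from 34 to 33. It also counts in the secondary endpoint. The effect is probably small, but the documents do not show it to be nil.

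**What to change.** One amendment, a few sentences:

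- In 6.2.8, cross-referenced in 7.1.7: *Permanently discontinue brentuximab for anaphylaxis of any grade.*
- In 6.2.9: *Regardless of grade, permanently discontinue brentuximab for SJS/TEN or confirmed PML, and hold for suspected PML.*
- In 5.2, after the grade 4 criterion: *except where Section 6.2 gives a specific rule.* Name anaphylaxis, SJS/TEN and confirmed PML there as always ending brentuximab, so that the exception cannot reopen them.

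The sponsor could instead let 5.2 govern and state in the 6.2.9 grade 4 row which events, if any, may resume. Without exceptions, that choice could cost roughly one of 34 patients the rest of protocol treatment in a curable disease, on the assumptions above. Letting Section 6.2 govern avoids this and is the cheaper route. The resume option need not be deleted for other grade 4 events.

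No new procedures, patients or staff are needed. The downside of the named stops is a very rare extra discontinuation, with alternative care discussed under 5.3.

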### 6.2.9 Other Brentuximab toxicities:

All other Grade 3-4 toxicity considered possibly, probably, or definitely related to brentuximab (Not including hematologic, cardiac, hepatic, gastrointestinal, peripheral nervous system, or alopecia).

Subjects will be removed from study treatment if a second episode of grade 3-4 toxicity occurs despite dose reduction according to table below.

CONFIDENTIAL

This document is confidential. Do not disclose or use except as authorized.

OTHER TOXICITY			
Grade	Brentuximab dose	AD doses	Comments
Grade 1	1.2 mg/kg (100%)	100%	
Grade 2	1.2 mg/kg (100%)	100%	
Grade 3	Withhold dose until toxicity is $\leq$ Grade 2 or has returned to baseline. Reduce the dose to 0.8 mg/kg. If a second dose reduction is required, dose will be reduced to 0.6 mg/kg.	Withhold dose until toxicity is $\leq$ Grade 2 or has returned to baseline, then resume at full dose.	The dose of brentuximab will not be re-escalated.
Grade 4	Withhold dose until toxicity is Grade $\leq 2$ or has returned to baseline, then reduce dose to 0.8 mg/kg and resume treatment, or discontinue at the discretion of the investigator. If a second dose reduction is required, dose will be reduced to 0.6 mg/kg, or discontinue at the discretion of the investigator.	Withhold dose until toxicity is Grade $\leq 2$ or has returned to baseline, then resume at full dose.	The dose of brentuximab will not be re-escalated.

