### 6.2.4 Hepatic Dysfunction

LFT's should be checked on the day of or day prior to treatment. No dose modification required for total bilirubin less than 1.5 mg/dL. Participants with total bilirubin of 1.5 to 2.0 mg/dL at study entry (and not due to Gilbert's disease) will be initiated at a 50% dose reduction of Adriamycin. For total bilirubin greater than 1.5 mg/dL on day 1 or 15, Adriamycin will be administered as below. Brentuximab vedotin will be held for ≥ grade 3 bilirubin (>3 mg/dL) until toxicity is ≤ grade 2. Upon restarting, the brentuximab dose will be reduced to 0.8 mg/kg. If a second dose reduction is required, dose will be reduced to 0.6 mg/kg. There are no dose reductions for dacarbazine based on bilirubin.

Total Bilirubin (mg/dL)	% Brentuximab Dose	% Adriamycin Dose	% Dacarbazine Dose
<1.5	100%	100%	100%
1.5 – 3.0	100%	50%	100%
>3.0-5.0	0%	25%	100%
>5.0	0%	0%	100%

CONFIDENTIAL

This document is confidential. Do not disclose or use except as authorized.

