#### **5.8 Hepatotoxicity**

Serious cases of hepatotoxicity, including fatal outcomes, have occurred in patients receiving ADCETRIS. Cases were consistent with hepatocellular injury, including elevations of transaminases and/or bilirubin. Cases have occurred after the first dose of ADCETRIS or after ADCETRIS rechallenge. Preexisting liver disease, elevated baseline liver enzymes, and concomitant medications may also increase the risk. Monitor liver enzymes and bilirubin. Patients experiencing new, worsening, or recurrent hepatotoxicity may require a delay, change in dose, or discontinuation of ADCETRIS.

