## **6.2 Post Marketing Experience**

The following adverse reactions have been identified during post-approval use of ADCETRIS. Because these reactions are reported voluntarily from a population of uncertain size, it is not always possible to reliably estimate their frequency or establish a causal relationship to drug exposure.

*Blood and lymphatic system disorders:* febrile neutropenia [see *Warnings and Precautions (5.3)*].

*Hepatobiliary disorders:* hepatotoxicity [see *Warnings and Precautions (5.8)*].

*Infections:* PML [see *Boxed Warning, Warnings and Precautions (5.9)*], serious infections and opportunistic infections [see *Warnings and Precautions (5.4)*].

*Metabolism and nutrition disorders:* hyperglycemia.

*Gastrointestinal disorders:* Pancreatitis (including fatal outcomes). Consider the diagnosis of pancreatitis for patients presenting with severe abdominal pain.

*Respiratory, thoracic and mediastinal disorders:* pulmonary toxicity [see *Warnings and Precautions (5.10)*].

*Skin and subcutaneous tissue disorders:* Toxic epidermal necrolysis, including fatal outcomes [see *Warnings and Precautions (5.11)*].

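### Section 6.2.9 excludes all hepatic and gastrointestinal toxicity, but 6.2.4 acts only on bilirubin and 6.2.6 holds for three events only, so a related grade 3 AST/ALT rise, vomiting, abdominal pain or pancreatitis meets no hold or reduction rule

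*Combined protocol and SAP*

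**What the plan says.** Section 6.2.9 is the residual rule for grade 3-4 toxicity that is possibly, probably or definitely related to brentuximab. At grade 3 it withholds brentuximab and AD until recovery, then resumes brentuximab at a reduced dose and AD at full dose. A second grade 3-4 episode despite reduction ends study treatment. The rule carries an exclusion by organ class: "Not including hematologic, cardiac, hepatic, gastrointestinal, peripheral nervous system, or alopecia".

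Section 6.2.4 is the liver rule. It requires testing before each dose: "LFT's should be checked on the day of or day prior to treatment". Its dosing text then refers only to bilirubin: "No dose modification required for total bilirubin less than 1.5 mg/dL", and "There are no dose reductions for dacarbazine based on bilirubin". The four rows of its table are bilirubin bands.

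Section 6.2.6 is the gastrointestinal rule. Under the line naming mucositis, dysphagia and diarrhea it states: "For $\geq$ Grade 3 gastrointestinal toxicities mentioned above, treatment will be held". Constipation gets a bowel regimen and no hold.

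The prescribing information bound into the document describes serious and fatal hepatotoxicity in its section 5.8: "Cases were consistent with hepatocellular injury, including elevations of transaminases and/or bilirubin". Under gastrointestinal disorders, its section 6.2 lists: "Pancreatitis (including fatal outcomes). Consider the diagnosis of pancreatitis for patients presenting with severe abdominal pain".

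**The concern.** Excluding an organ class from a residual rule is safe only if another rule covers that class. For liver and gut, the other rules cover part of it. Events in the remainder have no written hold or reduction, and they also escape the second-episode removal in 6.2.9.

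The main stake is patient safety: the uncovered events include hazards that the attached prescribing information describes as sometimes fatal. A lesser stake is consistency. With no written rule, sites will handle the same event differently, and discontinuation due to toxicity is part of a secondary endpoint (section 1.4.2) in a multi-site trial of 34 participants.

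**Working it through.** No power or error rate enters this point. The check traces each event through the rules, then counts what the documents offer on frequency.

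**1. Are these events in the excluded classes?** Section 6.1.3 lists raised AST and ALT under hepatic effects. Sections 6.1.2 and 6.1.3 list vomiting under gastrointestinal effects. The prescribing information lists abdominal pain (Table 2) and pancreatitis (section 6.2) under gastrointestinal disorders. On the documents' own classification, 6.2.9 excludes all of them.

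**2. Does 6.2.4 respond to AST or ALT?** Take a related grade 3 AST/ALT rise and read across the table:

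| Total bilirubin (mg/dL) | Brentuximab | Adriamycin | Dacarbazine | Changed by AST/ALT? |
|---|---|---|---|---|
| <1.5 | 100% | 100% | 100% | No |
| 1.5-3.0 | 100% | 50% | 100% | No |
| >3.0-5.0 | 0% | 25% | 100% | No |
| >5.0 | 0% | 0% | 100% | No |

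Any reduction comes from bilirubin. With bilirubin below 1.5 mg/dL, the only hepatic dosing text gives no modification. AST and ALT are nevertheless measured on every treatment day (section 8.2): 4 cycles × 2 = 8 visits, or 6 cycles × 2 = 12 visits.

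**3. Does 6.2.6 respond to the other gastrointestinal events?** Its hold is limited to the three events it names. Grade 3 vomiting, abdominal pain and pancreatitis are not among them.

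**4. Does a general clause supply a hold?** Section 5.2 ends therapy for unacceptable events, names related grade 4 events, and allows stopping on the investigator's opinion. It also ends therapy when a toxicity needs a delay beyond 2 weeks. Section 13.1.3 removes participants for unacceptable toxicity. These clauses govern stopping. None sets a hold or reduction at grade 3.

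**5. Comparison.** A related grade 3 rash is not in an excluded class, so 6.2.9 holds all three drugs and reduces brentuximab. A related grade 3 ALT rise with bilirubin below 1.5 mg/dL triggers neither step.

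**6. Frequency.** The table in 6.1.1 covers single-agent brentuximab (102 Hodgkin, 58 ALCL patients). It lists grade 3 or higher events seen in at least 2 patients of either group.
- AST/ALT: not listed, which implies at most 1/102 (1.0%) and at most 1/58 (1.7%).
- Abdominal pain, Hodgkin: 2/102 (2.0%) at grade 3 or higher, of which 1 was grade 4, so 2 − 1 = 1 at grade 3. ALCL: 1/58 (1.7%), with no grade 4.
- Vomiting: 0/102 and 2/58 (3.4%), with no grade 4.

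These counts are treatment-emergent, whereas 6.2.9 requires a relation to brentuximab. The documents give no rates for brentuximab with AD.

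**The case against.** The strongest reply is that silence is not an instruction. A reader might infer that the protocol orders full doses of all three drugs through a grade 3 transaminase rise. The documents do not support that. The 6.2.4 table says what bilirubin requires, just as the 6.2.3 table says what blood counts require, and nobody would read a 100% row for counts as overriding the neuropathy hold in 6.2.7. Section 6 calls its rules recommendations. The 2-week clause in 5.2 presupposes that doses can be delayed for any toxicity. The prescribing information (5.8) says hepatotoxicity may call for a delay, dose change or discontinuation. All of this stands.

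A reader might also infer that AST/ALT results lead to nothing. That is not supported either. Adverse events, including laboratory findings, are recorded and graded (10.2). Unexpected related grade 2-3 events and non-exempt grade 4 events are reportable (10.4.1), and the monitoring committee reviews toxicity quarterly (11.2).

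Three further replies stand. The AST/ALT entry limit of 2.5 × ULN concerns initial organ function, so its absence from the dosing rules is not a contradiction. Alopecia is excluded from 6.2.9 without a rule of its own, so the list is not purely a cross-reference. And if the secondary endpoint is read as a composite, a grade 3 ALT rise already counts, so only separate reporting of discontinuations could shift.

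None of these replies fills the gap. Discretion to stop and a duty to report are not a grade 3 hold, and the prescribing information gives no grade threshold for hepatotoxicity.

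**Conclusion.** The gap is real and follows from the stated exclusion. As written, a brentuximab-related grade 3 AST/ALT rise, vomiting, abdominal pain or pancreatitis triggers no hold or reduction rule in section 6.2. The finding is an uncovered set of events; it is not an order to dose through them.

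The size cannot be estimated for this regimen. The single-agent data suggest that such events are uncommon: no listed AST/ALT event, and 1 to 2 patients per study for the gastrointestinal events that appear. The case therefore rests on severity and on the mismatch between sections. No effect on the primary endpoint, power or type I error is shown.

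The conclusion assumes that raised AST/ALT counts as hepatic toxicity, as 6.1.3 has it, and that the event is judged at least possibly related to brentuximab.

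**What to change.** Reconcile the 6.2.9 exclusion list with the actual scope of 6.2.4 and 6.2.6, so that every related grade 3 event falls under exactly one stated rule. There are two drafting routes. One narrows the exclusion to the events those sections govern. The other extends 6.2.4 to address AST/ALT and 6.2.6 to address the remaining gastrointestinal events. Constipation needs a deliberate placement either way, since 6.2.6 gives it supportive care but no hold. The sponsor decides the clinical content; this review does not propose it.

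The edit is short and needs no new tests, because AST and ALT are already measured at every dose. It is still a substantive choice: narrowing the exclusion would bring the 6.2.9 hold and reduction into play for isolated transaminase rises. The likely cost is a few more holds or reductions.

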### **1.4 Endpoints**

- 1.4.1 Primary: Complete response rate (CRR) at end of treatment restaging, by the revised International Working Group Criteria (see appendix A)
- 1.4.2 Secondary:
- Rate of grade III and IV adverse events or discontinuation due to toxicity
  - Overall response rate (ORR) at end of treatment restaging
- 1.4.3 Exploratory:
- Failure-free survival (FFS)
  - Overall survival (OS)

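### Section 6.2.9 gives two incompatible instructions for a second related grade 3-4 event: removal from treatment in the text, 0.6 mg/kg or investigator discretion in the table

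*Combined protocol and SAP*

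**What the plan says.** Section 6.2.9 covers grade 3-4 toxicity at least possibly related to brentuximab, other than hematologic, cardiac, hepatic, gastrointestinal and peripheral nervous system events and alopecia. It contains two sets of instructions.

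- **Text above the table:** "Subjects will be removed from study treatment if a second episode of grade 3-4 toxicity occurs despite dose reduction according to table below".
- **Table, grades 1 and 2:** all drugs continue at 100%.
- **Table, grade 3, brentuximab:** hold, then resume at 0.8 mg/kg. "If a second dose reduction is required, dose will be reduced to 0.6 mg/kg". The row has no removal instruction.
- **Table, grade 4, brentuximab:** hold, then resume at 0.8 mg/kg or stop at discretion. "If a second dose reduction is required, dose will be reduced to 0.6 mg/kg, or discontinue at the discretion of the investigator".
- **Table, AD column, grades 3 and 4:** hold until the event has improved to grade 2 or less "or has returned to baseline, then resume at full dose".

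Three other sections bear on the point. Section 6.2.4 can produce a first reduction for raised bilirubin: "Upon restarting, the brentuximab dose will be reduced to 0.8 mg/kg". Section 6.2.7 can produce one for neuropathy, and it states when the next step applies: "If dose has already been reduced to 0.8 mg/kg, reduce dose to 0.6 mg/kg". Section 5.2 includes "other Grade 4 events felt to be related to brentuximab" among the unacceptable events that end therapy.

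**The concern.** A patient has a related grade 3 event in this class, recovers, and resumes at 0.8 mg/kg under the 6.2.9 table. A second grade 3 event in the class follows. The text says to stop all study treatment. The table says to continue brentuximab at 0.6 mg/kg with full-dose AD. Both apply to the same patient and they cannot both be followed.

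At stake is the treatment of a patient with recurrent severe drug-related toxicity in a multi-center trial. Two sites could act in opposite ways, each citing 6.2.9. The choice also affects assessment: under section 8.3 a patient who stops early is evaluated about 14 days after the last dose instead of 6 weeks, and a PET-CT from within 28 days of stopping can replace the repeat scan.

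**Working it through.** No stated figure in the plan rests on this rule, so there is nothing to reproduce. The check is a comparison of the texts, followed by the size of the difference.

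**Step 1. When can a second reduction arise inside this table?** Grades 1 and 2 carry full dose, so only a grade 3 or 4 event triggers a reduction here. If the first reduction (1.2 to 0.8 mg/kg) came from this table, the patient has already had one grade 3-4 event. A second reduction (0.8 to 0.6 mg/kg) then needs a second grade 3-4 event. That event meets the removal condition in the text.

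**Step 2. Compare the actions by route.**

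| Source of the 0.8 mg/kg dose | Next event in the 6.2.9 class | Text | Table |
|---|---|---|---|
| 6.2.9 table | second event, grade 3 | remove | 0.6 mg/kg, AD at full dose |
| 6.2.9 table | second event, grade 4 | remove | 0.6 mg/kg with AD at full dose, or stop, at discretion |
| 6.2.4 or 6.2.7 | first event, grade 3 | no removal | 0.6 mg/kg, AD at full dose |
| 6.2.4 or 6.2.7 | first event, grade 4 | no removal | 0.6 mg/kg with AD at full dose, or stop, at discretion |

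The first two lines conflict. The last two do not conflict within 6.2.9.

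**Step 3. Does section 5.2 settle it?** It favors stopping for a related grade 4 event, but it says nothing specific about a second grade 3 event.

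**Step 4. Size for one patient.** Inputs: two doses per 28-day cycle, so 8 doses in 4 cycles; 0.6 mg/kg brentuximab; 25 mg/m² Adriamycin; 375 mg/m² Dacarbazine. With *r* doses remaining, the table allows up to 0.6*r*, 25*r* and 375*r*. The text allows 0.

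- Second event after dose 4 of 8, *r* = 4: 4 × 0.6 = 2.4 mg/kg; 4 × 25 = 100 mg/m²; 4 × 375 = 1,500 mg/m².
- Earliest second event, after dose 2, *r* = 8 − 2 = 6: 3.6 mg/kg; 150 mg/m²; 2,250 mg/m².
- Second event after the last dose, *r* = 0: no difference.

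**Step 5. Size for the trial.** The documents give no rate for two such events in one patient. The per-patient rate *p* below is an assumption, shown as a range. Expected cases are 34*p*, and the chance of at least one is 1 − (1 − *p*)^34.

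| *p* (assumed) | Expected cases | Chance of at least one |
|---|---|---|
| 0.5% | 0.17 | 15.7% |
| 1% | 0.34 | 28.9% |
| 3% | 1.02 | 64.5% |

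**Step 6. Effect on endpoints.** The secondary safety endpoint in section 1.4 is "Rate of grade III and IV adverse events or discontinuation due to toxicity". Read as the composite it is written as, it does not move, because the patient already counts through the grade 3-4 events. If discontinuation is reported on its own, each case moves that rate by 1/34 = 2.9 percentage points (34 treated). The 34-patient design and the 31-response threshold in section 13.1.1 do not change.

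**The case against.** The strongest reply is that the two texts can be read together. The removal sentence is mandatory and the table step is conditional on a second reduction being needed; a patient already removed never needs one. The 0.6 mg/kg step still has a use, because 1.2, 0.8 and 0.6 mg/kg form one brentuximab ladder shared with 6.2.4 and 6.2.7, and the 6.2.7 and 6.2.9 tables bar re-escalation. Alternatively, a second episode might mean recurrence of the same toxicity, leaving 0.6 mg/kg for a different one. Stopping is also always open to the investigator under 5.2, and for grade 4 the table's discretion can be used to comply with the text. Finally, the remaining AD doses are part of the planned course and not excess exposure.

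Much of this stands. The conflict is confined to patients whose first reduction came from this table. The grade 4 half is weaker than the grade 3 half. The trial-level rate is assumed. The dose totals measure the gap between the two instructions and do not show harm.

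It does not remove the conflict. Neither limiting reading is written in 6.2.9, whereas 6.2.7 does write out when its further step applies. The two readings also lead to opposite actions: for a second event of a different kind, the first removes the patient and the second continues at 0.6 mg/kg. That stopping is always permitted does not tell a site whether continuing is also permitted.

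**Conclusion.** The concern holds; section 6.2.9 is wrong as written. For a patient reduced once under its table who has a second grade 3 event in the class, the text requires removal and the table requires continuation. For a second grade 4 event the text requires removal and the table makes it optional.

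The consequence is up to six further doses or none in a 4-cycle course, for a patient with recurrent severe related toxicity. The case is likely to be rare, and the trial-level range rests entirely on the assumed 0.5% to 3%. The composite safety endpoint, the sample size and the success rule are unaffected. It should be fixed because it is a conflict between two safety instructions, not because it threatens the trial's conclusion.

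**What to change.** Amend 6.2.9 so that one action applies. The cleanest choice is to keep the removal sentence and limit the 0.6 mg/kg wording in both the grade 3 and grade 4 rows to patients whose first reduction was made under 6.2.4 or 6.2.7. This keeps the conflict-free use of that step and does not add to the tension between the grade 4 row and section 5.2.

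The alternative is to change the sentence so that removal follows only a further grade 3-4 episode at 0.6 mg/kg. If a second episode is meant as recurrence of the same toxicity, 6.2.9 should say so. The clinical choice is the sponsor's. Since the grade 4 row permits resumption where 5.2 points to stopping, the same amendment could align those two.

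The cost is one sentence, or the brentuximab cells of two table rows, plus notice to sites. Aligning the grade 4 row with 5.2 would add a small edit. Sample size and analysis stay as they are.
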